### 5.1.2 Patient reported outcomes

#### 5.1.2.1 ZBPI

Each item of the ZBPI is considered for analysis.

Items related to assessment of pain (and “worst pain” in particular) are also categorized as:

- Mild pain [0 – 3[
- Moderate pain [3 – 7[
- Severe pain [7-10]

In addition, synthetized criteria are computed when all items concerned are filled:

- Mean of assessment of pain
- Mean of burden of pain. If one item out of the 7 is missing, the mean is computed on the 6 other items.

The change of quantitative criteria from Inclusion to phone interviews at M1, M3 (M6 and M9 for PHN cohort) are assessed as well: score at phone interview – score at inclusion.

### 5.1.2.2 EQ-5D-5L

Each item of the EQ-5D-5L is considered for analysis.

A total of 3125 ( $5^5$ ) possible health states can be defined through the 5 levels of answers of the 5 dimensions of the EQ-5D-5L.

A single index value, country-specific (France for this study), is used for valorizing each health state.

Since, at time of this SAP writing, no indexes exist for the EQ-5D-5L for France, the crosswalk value set from the EQ-5D-3L computed on a study on 3691 patients with different diseases and from different countries will be used, as recommended by the EuroQol group.

The change of quantitative criteria from Inclusion to phone interviews at M1, M3 (M6 and M9 for PHN cohort) are assessed as well: value at phone interview – value at inclusion.

### 5.1.3 Health care resources

All health care resources items are considered for analysis, in addition to the costs assessments.

Medications are coded according to the Vidal dictionary. The Anatomic and Therapeutic Class (ATC) are used for categorizing treatments by:

- Anatomic class (first digit of the ATC class)
- Therapeutic class (three first digit of the ATC class)

In addition, the number of different treatments (according to the therapeutic class) is computed by time frame.

Analgesics are also classified according to their class (1, 2, 3, or local), based on names and doses of the products.

### 5.1.4 Costs assessments

The costs are evaluated by time frame:

- At inclusion
- Cumulatively up to 1 month
- Cumulatively up to 3 months
- Cumulatively from 1 to 3 months
- Cumulatively up to 6 months for PHN cohort
- Cumulatively from 3 to 6 months for PHN cohort

- Cumulatively up to 9 months for PHN cohort
- Cumulatively from 6 to 9 months for PHN cohort The type of costs evaluated are:
- Direct medical costs: hospital stays, emergency room visits, medical visits, medications - Indirect costs: patient sick leave

#### 5.1.4.1 *Direct medical costs*

##### 5.1.4.1.1 Medications

Based on the full description of the treatment name on the box,

- described by the physician at inclusion as taken by the patient before inclusion, - and given by the patient during phone interviews, the cost of the treatment by box (tax included) is retrieved thanks to the Vidal dictionary (2016).

The cost by treatment is equal to the number of boxes multiplied by the cost of the box.

The part reimbursed by the French social insurance is retrieved as well by the French Vidal dictionary.

The medication costs for one patient are the sum of all the costs of the medications taken by the patient by time frame.

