## 2. POPULATIONS

### 2.1 Patients' population

To be included in the HZ cohort, patients had to fulfill all the following criteria:

- Patients with a first visit for a diagnosis of HZ and who attend the clinic within two weeks of the start of HZ symptoms (defined as unilateral pain accompanied by a unilateral rash without alternative diagnosis)
- Without any history of previous HZ
- $\geq 50$  years old
- Who agree to participate and signed informed consent
- Able to understand the study, to complete self-administered questionnaires (alone or with the help of a relative) and to answer phone interviews

All patients of the HZ cohort presenting PHN 3 months after onset of the HZ rash onset should be included in the PHN cohort.

PHN was defined as the presence of HZ-associated severe pains:  $\geq 3$  of the ZBPI item "worst pain", completed during the phone interview of the patient at 3 months  $\pm 1$  week.

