### 3.3 Health care resources

#### 3.3.1 *Medical treatments for HZ and its consequences*

Treatments prescribed and taken by the patient are recorded at several time frames:

- Treatments bought by the patient before the inclusion visit (recorded by the physician on the CRF at inclusion visit)
- Treatments prescribed by the physician at the end of the inclusion visit - Treatments taken by the patient, recorded during phone interviews:
  - o Between inclusion and 1 month
  - o Between 1 month and 3 months
  - o Between 3 months and 6 months (for the PHN cohort)
  - o Between 6 months and 9 months (for the PHN cohort)

The following items are recorded, for each treatment: treatment name, dosage (mg), number of boxes, number of tablets contained in one box.

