##### 5.1.4.1.2 Medical visits

The costs of the medical visits are assessed according to the type of medical specialization visited (general practitioner, specialist).

Specialty	Cost (€) tax included	Part reimbursed by SS	Source
General Practitioner	23.00	70% - 1€	https://www.ameli.fr/l-assurance-maladie/statistiques-et-publications/donneesstatistiques/professionnels-de-santeliberaux/honoraires/honoraires-totaux-etmoyens.php?source=2014

Dermatologist	46.00	70% - 1€	https://www.ameli.fr/l-assurance-maladie/statistiques-et-publications/donneesstatistiques/professionnels-de-santeliberaux/honoraires/honoraires-taux-etmoyens.phpsource - 2014
Ophthalmologist	46.00	70% - 1€	https://www.ameli.fr/l-assurance-maladie/statistiques-et-publications/donneesstatistiques/professionnels-de-santeliberaux/honoraires/honoraires-taux-etmoyens.phpsource - 2014
Rheumatologist	46.00	70% - 1€	https://www.ameli.fr/l-assurance-maladie/statistiques-et-publications/donneesstatistiques/professionnels-de-santeliberaux/honoraires/honoraires-taux-etmoyens.phpsource - 2014
Pain management ward	46.00	70% - 1€	https://www.ameli.fr/l-assurance-maladie/statistiques-et-publications/donneesstatistiques/professionnels-de-santeliberaux/honoraires/honoraires-taux-etmoyens.phpsource - 2014
Osteopath	50.00	70% - 1€	Mean assessment

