#### 5.1.4.3 *Approaches*

Two approaches are considered for the analysis:

- The Societal approach: This approach is the most global approach, and includes the sum of all costs.
- The Payer approach: part paid by the French social security

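### The payer cost credits Social Security with a share of drugs bought before the inclusion visit and of osteopath visits, without support that it paid them; both components may be overstated

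*SAP*

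**What the plan says.** Section 5.1.4.3 defines the second cost perspective as "The Payer approach: part paid by the French social security". Section 5.2.2.3 sums direct and indirect costs under both perspectives.

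Section 5.1.4.1.1 costs two groups of drugs. One is those "described by the physician at inclusion as taken by the patient before inclusion"; the other is those reported by the patient by phone. It then adds: "The part reimbursed by the French social insurance is retrieved as well by the French Vidal dictionary". The look-up is by product and applies to both groups alike.

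Section 3.3.1 calls the first group "Treatments bought by the patient before the inclusion visit" and lists it apart from drugs prescribed at that visit. Section 2.1 makes the inclusion visit a first diagnostic visit: "Patients with a first visit for a diagnosis of HZ". The items section 3.3.1 records for each treatment are the product name, strength, box count and box size.

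In the unit-cost table of section 5.1.4.1.2 (which runs over a page break), every row but one cites a health-insurance fee page. The exception is the osteopath: 50.00 EUR, source "Mean assessment", with the same payer share as all other rows, 70% minus 1 EUR.

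**The concern.** A listed reimbursement rate says what the insurer would pay if its conditions were met. It does not say that the insurer paid. Section 3.3.1 separates drugs acquired before the visit from drugs prescribed at it, and the visit is the first for the diagnosis. Purchase without a prescription is therefore a natural reading for at least some of the pre-inclusion drugs, though the SAP does not say so. The plan nevertheless books the listed rate as a payment for all of them, and the recorded items give no means of correcting this.

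The osteopath row raises a similar question. A price set by general assessment rather than taken from an insurance source still receives a full Social Security share.

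Costs are the primary objective (section 1.1), and the payer approach is one of the two ways in which they are reported. A share credited without payment would go straight into that result.

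**Working it through.** The SAP states no payer amount in euros for any drug or visit, so there is no planned figure to reproduce. The amounts below follow from its rules.

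**Visits.** Inputs: unit costs and share from the table in section 5.1.4.1.2. Payer amount = 0.70 × unit cost − 1.

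| Provider | Unit cost (EUR) | Payer amount (EUR) | Price source |
|---|---|---|---|
| GP, acupuncturist | 23.00 | 0.70 × 23 − 1 = 15.10 | insurance fee page |
| Dermatologist, ophthalmologist, rheumatologist, pain ward | 46.00 | 0.70 × 46 − 1 = 31.20 | insurance fee page |
| Osteopath | 50.00 | 0.70 × 50 − 1 = 34.00 | general assessment |

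The one row without an insurance source thus carries the largest payer amount: 34.00 − 31.20 = 2.80 EUR above a specialist visit, and 34.00 / 15.10 = 2.25 times a GP visit. If the true share lies between nil and the tabled one, the overstatement per visit is 0 to 34.00 EUR.

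Section 1.4.2 expects about 100 subjects. With that denominator, each osteopath visit in the whole cohort adds up to 34.00 / 100 = 0.34 EUR to the mean payer cost. Ten visits (an assumed count; the SAP gives none) would add up to 3.40 EUR. Section 5.2.2.3 restricts the cost analysis to patients with both the 1-month and 3-month interviews. If that leaves fewer than 100, the effect per visit is proportionately larger.

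**Drugs bought before inclusion.** For one box with price p and listed rate r, the plan books p × r. If the box was reimbursed at that rate, the error is 0. If it was not reimbursed, the error is p × r. A product listed as non-reimbursed has r = 0 and causes no error. The error for this component can therefore only raise the payer cost. The SAP gives neither p nor r. Purely for scale, an assumed price of 2 to 10 EUR and an assumed rate of 0 to 65% give 0 to 10 × 0.65 = 6.50 EUR per box.

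**Where it shows.** Section 5.1.4 reports costs at inclusion as a separate time frame. Section 5.1.4.1.1 does not cost drugs prescribed at the inclusion visit as such, and phone-reported drugs start after inclusion (section 3.3.1). Drugs obtained before the visit are therefore the only drug component of that figure. The SAP does not name their time frame, but inclusion is the only one that fits. Beside them stands the inclusion visit, with a payer amount of 15.10 EUR (GP) or 31.20 EUR (dermatologist or ophthalmologist). In the cumulative 3- to 9-month costs the same amount is diluted by later spending.

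**The case against.** A reader might infer that the payer cost as a whole is overstated. The SAP does not support that, for four reasons.

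- It nowhere says that unprescribed drugs or osteopath visits go unreimbursed. It only leaves the credited share without a basis.
- A first visit for an HZ diagnosis is not necessarily a first medical contact. Section 3.1 records prodromal pain, fever and malaise, and a drug prescribed for these before the diagnosis would also count as bought before inclusion. Bought does not mean unprescribed.
- Other rules may pull the payer total down. Radiologist visits are not costed (section 5.1.4.1.2), and neurologist visits are recorded (section 3.3.3) but have no row in the unit-cost table.
- No counts of pre-inclusion boxes or osteopath visits are given. The effect may be negligible, particularly against 3 to 9 months of costed follow-up.

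The contrast for the osteopath is also narrower than it first looks. The links in the other rows point to fee pages, so on their face they source the price. No row cites a separate source for the share.

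All of this stands, and it limits the claim to two components that are unsupported and may be too high. It does not justify either rule. Possible gaps elsewhere in the opposite direction do not turn a listed rate into a payment, and the missing prescription status remains missing.

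It is also tempting to scale the drug error by assuming some self-bought fraction of all drug spending. The SAP gives no such fraction, and it would cover a broader group than the pre-inclusion purchases at issue here.

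**Conclusion.** The point holds for two components of the payer cost. The plan credits Social Security with the listed share of drugs bought before inclusion, with no prescription or reimbursement status recorded, and with 34.00 EUR for each osteopath visit whose price has no insurance source. Neither credit is shown to meet the SAP's own definition of payer cost.

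The possible overstatement is 0 to 34.00 EUR per osteopath visit and 0 to price times listed rate per pre-inclusion box. The upper ends apply only if nothing was reimbursed, which is an assumption and not something the SAP states. The effect on the mean is unknown. The osteopath part is likely to be small, and the drug part is most exposed in the cost at inclusion. The direction of error in the total payer cost is not established, and the societal cost is not affected.

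**What to change.** Make three changes to the payer approach:

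1. In section 5.1.4.1.1, credit no payer share to drugs bought before the inclusion visit unless they are known to have been prescribed. With the items now recorded, that will in practice mean a share of 0.
2. In section 5.1.4.1.2, set the osteopath payer share to 0 unless a Social Security source for it is cited.
3. In section 5.2.2.3, report the payer cost both ways, with the shares as planned and with both at nil, and present the two as bounds for these components. Do this for the inclusion time frame as well as the cumulative ones.

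Nil is itself an assumption, which is why both results should be shown. Restricting drugs to the inclusion prescription list is not a suitable alternative, because it would omit drugs prescribed at later visits.

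The cost is two rule lines and one extra column, with no new data. The main payer figure may come out slightly lower, and societal costs stay as they are.

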##### 5.1.4.1.2 Medical visits

The costs of the medical visits are assessed according to the type of medical specialization visited (general practitioner, specialist).

Specialty	Cost (€) tax included	Part reimbursed by SS	Source
General Practitioner	23.00	70% - 1€	https://www.ameli.fr/l-assurance-maladie/statistiques-et-publications/donneesstatistiques/professionnels-de-santeliberaux/honoraires/honoraires-totaux-etmoyens.php?source=2014

Dermatologist	46.00	70% - 1€	https://www.ameli.fr/l-assurance-maladie/statistiques-et-publications/donneesstatistiques/professionnels-de-santeliberaux/honoraires/honoraires-taux-etmoyens.phpsource - 2014
Ophthalmologist	46.00	70% - 1€	https://www.ameli.fr/l-assurance-maladie/statistiques-et-publications/donneesstatistiques/professionnels-de-santeliberaux/honoraires/honoraires-taux-etmoyens.phpsource - 2014
Rheumatologist	46.00	70% - 1€	https://www.ameli.fr/l-assurance-maladie/statistiques-et-publications/donneesstatistiques/professionnels-de-santeliberaux/honoraires/honoraires-taux-etmoyens.phpsource - 2014
Pain management ward	46.00	70% - 1€	https://www.ameli.fr/l-assurance-maladie/statistiques-et-publications/donneesstatistiques/professionnels-de-santeliberaux/honoraires/honoraires-taux-etmoyens.phpsource - 2014
Osteopath	50.00	70% - 1€	Mean assessment
Acupuncturist	23.00	70% - 1€	https://www.ameli.fr/l-assurance-maladie/statistiques-et-publications/donneesstatistiques/professionnels-de-santeliberaux/honoraires/honoraires-taux-etmoyens.phpsource - 2014

The cost for radiologists, healers, magnetizers will not be valorized.

The cost of the inclusion visit is evaluated according to the specialty of the investigator: general practitioner, dermatologist, ophthalmologist.

The cost of each medical visit recorded through phone interviews is evaluated according to the specialty visited.

The medical visit costs for one patient are the sum of all the costs of the visits made by the patient by time frame.

#### 5.1.4.1.3 Emergency room visits

No emergency room visits at all recorded in this study.

#### 5.1.4.1.4 Hospital stays

No hospital stays at all recorded in this study.

#### 5.1.4.2 *Indirect costs*

The cost of daily allowance is assessed as the overall national mean for France.

The total sum paid in France by the Social Security for daily allowances in 2012 ( $6.4 \cdot 10^9$  €) is divided by the total number of days with allowance paid in France ( $204 \cdot 10^6$  days) = 31.37 € (source: Cours des Comptes: ). The cost is acutalized to 2016, by multiplying the value by 1.0438 (evolution of cost of days of allowance from 2012 to 2016 according to DREES – PPD

██████████) = 32.74 €.

The sum of the days missed for HZ and its consequences by time frame is then multiplied to the daily allowance cost obtained.

#### 5.1.4.3 *Approaches*

Two approaches are considered for the analysis:

- The Societal approach: This approach is the most global approach, and includes the sum of all costs.
- The Payer approach: part paid by the French social security

## 5.2 Statistical methods

### 5.2.1 Disposition of physicians and patients

A flowchart will describe the physician recruitment process (contacted, refusing to participate and reasons, agreeing to participate, including patients in the HZ cohort and PHN Cohort).

Number of patients included, number and percentage of the analyzable patient population (reported on the number of patients included), will be presented globally, for patients with PHN and for patients with HZ without any PHN. Reasons for exclusion from the analyzable population are described as well (inclusion criteria not met).

### 5.2.2 Analyses

#### 5.2.2.1 Physicians' characteristics

Age and gender of active physicians having included at least one analyzable patient, will be described globally and by specialty according to the general statistical approach described in section 4.

The national statistics of age and gender published by the Department for Evaluation and statistics of the French Health Ministry for 2016 (DREES – source:

<http://www.data.drees.sante.gouv.fr/ReportFolders/reportFolders.aspx>) for France mainland will be used as descriptive reference figures for the three specialties of investigators recruited in this study (general practitioners, dermatologists, ophthalmologists).

#### 5.2.2.2 Patients' data

All analyses (see section 5.1) will be conducted globally for the HZ and for the PHN cohorts. The analysis of the HZ cohort will also be performed according to:

- gender
- classes of age: < 70 years / ≥70 years

Due to the very small sample size expected for the PHN cohort, no further subgroup of this cohort will be considered.

Patients' profiles will be produced for each of the patients of the PHN cohort.

#### 5.2.2.2.1 Clinical variables

Clinical variables (see section 5.1.1) will be analyzed in a descriptive way according to the general statistical approach described in section 4.

#### 5.2.2.2.2 Patient reported outcomes

PRO variables (see section 5.1.2) will be analyzed in a descriptive way according to the general statistical approach described in section 4, by time frame (inclusion, 1 month, 3 months, and for PHN: 6 months and 9 months).

Analysis of evolutions from inclusion will also be conducted by time frame, by use of the Wilcoxon signed rank test for quantitative criteria and by use of the Mc Nemar's test for binary criteria in the HZ cohort.

Spaghetti plots will be produced for describing the evolutions in the PHN cohort.

In addition, for the analysis of the EQ-5D-5L indexes, the reference value of the index for France for EQ5D-3L indexes (Chevalier J, 2013) is used for assessing the average loss in quality of life at inclusion and by time frame.

As a sensitivity analysis, means and 95%CI of the means of the EQ-5D-5L index will also be estimated by a generalized linear model, with Gamma distribution and log as link function.

Consistency between PRO measurements will be assessed by scatter plots crossing the individual items of the ZBPI with the individual items of the EQ-5D-5L, at baseline, at 1 month and at 3 months, for the HZ cohort.

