### 1.1 Objectives

The primary objective is to evaluate Herpes Zoster (HZ)-related and Post Herpetic Neuralgia (PHN)-related direct medical costs and indirect costs during a 9 months period (overall, by gender and classes of age) among people  $\geq 50$  years old in France.

Secondary objectives are:

- To describe HZ and PHN pain severity during a 9 months period (overall and by classes of age)
- To evaluate the impact of HZ and PHN on the quality of life of patients during a 9 months period (overall by gender and by classes of age)

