## 1.2 Study design

This is an observational, prospective cohort study of patients  $\geq 50$  years old with a Herpes Zoster (HZ) diagnosis, carried out by a French national random sample of community first line practitioners concerned by HZ diagnosis: general practitioners (GPs), dermatologists and ophthalmologists.

Patients  $\geq 50$  years old with a primary HZ diagnosis (no earlier case of HZ) were included in the **HZ cohort** during a one-year inclusion period.

[figure not shown]
All patients of the HZ cohort presenting Post Herpetic Neuralgia (PHN) 3 months (defined as the presence of HZ-associated severe "worst" pain: pain  $\geq 3$  from ZBPI item "worst pain") after HZ rash onset symptoms were included secondarily in the **PHN cohort**.

Patients of the HZ cohort were followed-up for 3 months using phone interviews with a nurse at 1 month (+/- 3 days) and 3 months (+/- 1 week) after HZ rash onset.

Patients of the PHN cohort were followed up for another 6 months period using phone interviews with a nurse a 6 months (+/- 1 week) and 9 months (+/- 1 week) after HZ rash onset.

Page

Graph 1: Study Design

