### 1.4.2 *Number of subjects*

Despite the corrective actions conducted in the patients' recruitment process, the final number of subjects expected to be included in the study is around 100.

With a sample of 100 subjects, a precision between  $\pm 4.9\%$  and 39.2% is obtained for a standard deviation between  $\frac{1}{4}$  and 2 times the mean.

**Table 2: Precision of a 95% CI for a continuous variable, taking into account the standard deviation and a sample size of 100 patients, according to the normal distribution of the mean**

Sample size (n)	Standard Deviation (SD as % of the mean)					
	1/4	2/4	3/4	1	1,5	2
100	4,9%	9,8%	14,7%	19,6%	29,4%	39,2%

$\pm 1,96 \cdot SD / \sqrt{n}$ , with SD the standard deviation and n the sample size.

All the analyses will be performed as initially planned, except when the number of patients in a subgroup of interest is below 5.

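### Quality-of-life loss is taken against one national EQ-5D-3L value with no age or sex matching, so any gap between that value and the patients' own norm is reported as herpes zoster burden

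*SAP*

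**What the plan says.** SAP section 5.2.2.2.2 is the only place that specifies a loss in quality of life. It takes "the reference value of the index for France for EQ5D-3L indexes", cites one publication, and says that this value "is used for assessing the average loss in quality of life at inclusion and by time frame". The noun is singular and the value is national. Neither this section nor any other gives the number, the population behind it, age or sex classes, or weighting to the cohort.

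The patients' own index is obtained by mapping the five-level answers through "the crosswalk value set from the EQ-5D-3L computed on a study on 3691 patients" (section 5.1.2.2). The same section defines change as "value at phone interview – value at inclusion".

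The cohort is restricted to people aged 50 or more with a first episode of HZ (sections 1.2 and 2.1). Section 1.1 makes the impact on quality of life a secondary objective, "overall by gender and by classes of age". Section 5.2.2.2 has the HZ cohort analysed by gender and by "classes of age: < 70 years / ≥70 years". It plans no subgroups for the post-herpetic neuralgia cohort.

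**The concern.** A loss is only as good as the state it is measured from. Here that should be the utility these patients would have had without HZ. Health utility in the general population can differ by age and sex, and a single national figure takes no account of either. Where the figure differs from the norm for people of the cohort's age and sex, the difference enters the reported loss at every visit, and recruiting more patients does not reduce it.

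The problem is sharper in the strata. If older patients have lower utility than younger patients for reasons unrelated to HZ, one constant makes that look like a heavier burden of HZ in the older class. The same applies to gender. What is at stake is the interpretation of a stated secondary objective. The primary cost objective is not affected.

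**Working it through.** **The plan's own precision figure.** The SAP states no figure for the loss. The nearest is Table 2 in section 1.4.2, the half-width of a 95% CI for a mean, 1.96 × SD / √n, with n = 100 ("the final number of subjects expected to be included in the study is around 100").
- SD = 1/4 of the mean: 1.96 × 0.25 / 10 = 4.9%.
- SD = 2 times the mean: 1.96 × 2 / 10 = 39.2%.

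Both ends agree with the SAP.

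**What the reported loss estimates.** Let R be the single reference, N the norm for the age and sex mix of the group analysed, and L the true mean loss due to HZ. Suppose that without HZ the group would sit at its norm.
- Mean index = N − L.
- Reported loss = R − (N − L) = L + (R − N).

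The bias is R − N. It is zero only if the reference equals the group's own norm.

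**Illustration for the whole cohort.** Neither R nor N is in the SAP, so these gaps are assumptions, with an assumed true loss of 0.10:

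| R − N (assumed) | Reported loss | Share not due to HZ |
|---|---|---|
| 0 | 0.10 | 0% |
| 0.02 | 0.12 | 0.02 / 0.12 = 17% |
| 0.05 | 0.15 | 0.05 / 0.15 = 33% |
| 0.10 | 0.20 | 0.10 / 0.20 = 50% |

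A negative gap would understate the loss in the same way.

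**Scale against sampling error.** Assume a mean index of 0.6 to 0.8 and SD = 1/4 of the mean. The half-width at n = 100 is 0.049 × 0.6 = 0.029 to 0.049 × 0.8 = 0.039. A gap of 0.05 would exceed it, and the interval would give no sign of it.

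**Contrast between strata.** With one R in both age classes:
- loss(≥70) − loss(<70) = [R − mean(≥70)] − [R − mean(<70)] = mean(<70) − mean(≥70).

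R cancels. Substituting mean = N − L in each class gives the true difference in loss plus N(<70) − N(≥70). With equal true losses, an assumed norm difference of 0, 0.03, 0.05 or 0.10 shows as an excess loss of 0, 0.03, 0.05 or 0.10 in the older class. This result needs no figure from the cited source and holds for gender too.

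**Does anything else in the plan repair it?**
- Change from inclusion does not. Under section 2.1 patients are seen within two weeks after symptoms start, so the starting value is already affected by HZ. The change describes recovery.
- The Gamma sensitivity model in section 5.2.2.2.2 re-estimates the mean index and leaves the comparator as it is.

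**The case against.** The SAP sentence is short and a good deal has to be read into it. It gives no formula and speaks of an average loss, so subtraction patient by patient is an inference. Its use in subgroups is also inferred: section 5.2.2.2 refers back to the variables of section 5.1, and section 5.1.2.2 lists the items, the index and the change, but not the loss. No test or model between age classes or genders is planned. The constant adds no new error to a subgroup contrast, since it cancels and the raw means are reported anyway. The cited source may contain age- and sex-specific values that the sponsor means to use.

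Most of this stands as a limit on the claim. It does not remove the point. Section 1.1 asks for the quality-of-life impact by gender and age class, so stratified reporting is the natural reading. Because the constant cancels, calling the result a loss in each stratum gives a raw difference in means a meaning that it lacks. If matched norms are intended, the SAP has to say so.

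A reader might go further and infer that the reference is an all-adult average, so that the loss is certainly overstated, most of all from age 70, and that fully recovered patients would still show a loss at 3 months. The SAP does not describe the reference population, so it supports neither that direction nor any size. A reader might also fault the use of a three-level reference for a five-level questionnaire. That is not an error here, because the crosswalk puts the patients' values on the three-level scale.

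**Conclusion.** The point holds in limited form. One unmatched national value is the wrong comparator for a cohort aged 50 or more whose quality-of-life impact is wanted by age and gender. The reported loss is L + (R − N), and differences in loss between strata carry the whole background difference in utility. Both statements follow from the definition, given that patients would otherwise sit at the norm for their age and sex.

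The size and sign of R − N cannot be found from the SAP; the range of 0 to 0.10 is illustrative only. Even matched norms would leave differences in comorbidity between the patients and the general population inside the loss. The raw index, the change scores and the pain results are unaffected. For a descriptive secondary output this should be corrected before analysis, but it does not threaten the study's main result.

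**What to change.** In section 5.2.2.2.2, define the loss as the French reference value for the patient's age class and sex minus the observed index, averaged over patients at each time frame. Equivalently, use norms weighted to the age and sex mix of the patients with an index at that time frame, overall and within each stratum. State the values, their age classes and the population they come from.

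If such norms are not available:
- label the result *difference from the national reference value*;
- do not present it as loss by age or gender;
- describe change from inclusion as recovery from acute HZ. It should not be promoted to the main measure of impact, because it starts after onset.

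The cost is a small lookup table in place of one constant and a few lines of SAP text. No new data are needed: gender and month and year of birth are collected at inclusion (section 3.1), and age is already derived (section 5.1.1).
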